#### 5.1.2 RP2D

Once 6 evaluable patients have been enrolled at a dose-level that is determined to be the MTD (according to the criteria outlined in Section 13.1) the observation period will be extended by 30 days in those 6 patients. If no more than 1 of 6 subjects experiences a DLT at this dose level, including in the extended observation window, the RP2D is equal to the MTD, and the expansion cohort will be treated at this dose level. If more than 1 of 6 subjects experiences a DLT at this dose level, including in the extended observation window, the expansion cohort will be enrolled in the next lower dose level to further confirm tolerability, which may then be declared the

RP2D.

### 5.1.3 Dose to be used for expansion

Dose escalation has been completed as of Amendment 10. The dose to be used for expansion is 100 mg triapine PO daily in combination with cisplatin based chemoradiation as described in this protocol. Data supporting this dose decision are detailed below and have been discussed with the CTEP Medical Monitor.

#### 5.1.3.1 Safety

The addition of oral triapine to standard of care cisplatin based chemoradiation was safe. There were no treatment related deaths.


Beyond the DLTs described above, the regimen was well tolerated with expected hematologic events in the context of known baseline toxicity data for standard of care cisplatin base chemoradiation. Among the nine evaluable patients, seven experienced at least one grade 3 toxicity, including lymphocyte decrease (n=7), anemia (n=4), neutrophil count decrease (n=4), white blood cell count decrease (n=4), platelet count decreased (n=1), hypertension (n=1), hyponatremia (n=1). A comprehensive list of adverse events is outlined in Table below.

**Adverse Events by Frequency during the dose escalation of NCI 9892.**

AEFamily	AETerm	Grade1	Grade2	Grade3	Grade4	Total
GENERAL/ADM. SITE CONDITIONS	Fatigue	7 (70%)	3 (30%)			10 (100.0%)
GI DISORDERS	Nausea	10 (100%)				10 (100.0%)
BLOOD/LYMPH DISORDERS	Anemia		4 (40%)	5 (50%)		9 (90.0%)
GI DISORDERS	Diarrhea	7 (70%)	2 (20%)			9 (90.0%)
INVESTIGATIONS	Lymphocyte count decreased		1 (10%)	5 (50%)	3 (30%)	9 (90.0%)
METABOLISM & NUTRITION	Hypomagnesemia	6 (60%)	1 (10%)			7 (70.0%)
METABOLISM & NUTRITION	Hyponatremia	6 (60%)		1 (10%)		7 (70.0%)
INVESTIGATIONS	Neutrophil count decreased	2 (20%)		3 (30%)	2 (20%)	7 (70.0%)
INVESTIGATIONS	White blood cell decreased		2 (20%)	3 (30%)	2 (20%)	7 (70.0%)
BLOOD/LYMPH DISORDERS	Blood/Lymph - Other - Methemoglobinemia	1 (10%)	4 (40%)	1 (10%)		6 (60.0%)
INVESTIGATIONS	Platelet count decreased	3 (30%)	2 (20%)	1 (10%)		6 (60.0%)
RENAL & URINARY DISORDERS	Urinary frequency	5 (50%)	1 (10%)			6 (60.0%)
GI DISORDERS	Gastroesophageal reflux disease	2 (20%)	3 (30%)			5 (50.0%)
METABOLISM & NUTRITION	Hypocalcemia	5 (50%)				5 (50.0%)
EAR & LABYRINTH	Tinnitus	5 (50%)				5 (50.0%)
GI DISORDERS	Vomiting	5 (50%)				5 (50.0%)
GI DISORDERS	Constipation	4 (40%)				4 (40.0%)
RENAL & URINARY DISORDERS	Hematuria	3 (30%)	1 (10%)			4 (40.0%)
METABOLISM & NUTRITION	Hyperglycemia	4 (40%)				4 (40.0%)
METABOLISM & NUTRITION	Hypokalemia	3 (30%)		1 (10%)		4 (40.0%)
METABOLISM & NUTRITION	Anorexia	3 (30%)				3 (30.0%)
GI DISORDERS	Bloating	3 (30%)				3 (30.0%)
NERVOUS SYSTEM	Dizziness	3 (30%)				3 (30.0%)
RESPIRATORY/THORACIC/MEDIASTINAL	Dyspnea	2 (20%)	1 (10%)			3 (30.0%)
GENERAL/ADM. SITE CONDITIONS	Fever	2 (20%)	1 (10%)			3 (30.0%)
NERVOUS SYSTEM	Headache	3 (30%)				3 (30.0%)
VASCULAR DISORDERS	Hypertension	1 (10%)	1 (10%)	1 (10%)		3 (30.0%)
PSYCHIATRIC DISORDERS	Insomnia	3 (30%)				3 (30.0%)
RENAL & URINARY DISORDERS	Renal & urinary disorders - Other - Dysuria	3 (30%)				3 (30.0%)
GI DISORDERS	Abdominal pain	1 (10%)	1 (10%)			2 (20.0%)
BLOOD/LYMPH DISORDERS	Blood/Lymph - Other - Thrombocytopenia	2 (20%)				2 (20.0%)
METABOLISM & NUTRITION	Dehydration		2 (20%)			2 (20.0%)
GENERAL/ADM. SITE CONDITIONS	Edema limbs	2 (20%)				2 (20.0%)
MUSCULOSKELETAL/CONNECTIVE TISSUE	Generalized muscle weakness	2 (20%)				2 (20.0%)
METABOLISM & NUTRITION	Hypoalbuminemia	2 (20%)				2 (20.0%)

[figure not shown]
INVESTIGATIONS	Investigations - Other, specify - Fogginess	2 (20%)				2 (20.0%)
CARDIAC DISORDERS	Sinus tachycardia	1 (10%)	1 (10%)			2 (20.0%)
INFECTIONS & INFESTATIONS	Urinary tract infection		1 (10%)	1 (10%)		2 (20.0%)
RENAL & URINARY DISORDERS	Urinary urgency	2 (20%)				2 (20.0%)
REPRODUCTIVE & BREAST DISORDERS	Vaginal hemorrhage	2 (20%)				2 (20.0%)
REPRODUCTIVE & BREAST DISORDERS	Vaginal pain	2 (20%)				2 (20.0%)
INVESTIGATIONS	Weight loss	2 (20%)				2 (20.0%)
INVESTIGATIONS	ALT increased	1 (10%)				1 (10.0%)
MUSCULOSKELETAL/CONNECTIVE TISSUE	Arthralgia	1 (10%)				1 (10.0%)
MUSCULOSKELETAL/CONNECTIVE TISSUE	Back pain	1 (10%)				1 (10.0%)
RENAL & URINARY DISORDERS	Bladder spasm	1 (10%)				1 (10.0%)
BLOOD/LYMPH DISORDERS	Blood/Lymph - Other - Increased Medthemoglobin Level		1 (10%)			1 (10.0%)
BLOOD/LYMPH DISORDERS	Blood/Lymph - Other - Increased Methemoglobin		1 (10%)			1 (10.0%)
BLOOD/LYMPH DISORDERS	Blood/Lymph - Other - Methameoglobinemia		1 (10%)			1 (10.0%)
BLOOD/LYMPH DISORDERS	Blood/Lymph - Other - Methemoglobin Increase		1 (10%)			1 (10.0%)
BLOOD/LYMPH DISORDERS	Blood/Lymph - Other - Methemoglobinmina		1 (10%)			1 (10.0%)
EYE DISORDERS	Blurred vision	1 (10%)				1 (10.0%)
CARDIAC DISORDERS	Cardiac disorders - Other - Chest Tightness	1 (10%)				1 (10.0%)
CARDIAC DISORDERS	Chest pain - cardiac	1 (10%)				1 (10.0%)
GENERAL/ADM. SITE CONDITIONS	Chills	1 (10%)				1 (10.0%)
RENAL & URINARY DISORDERS	Cystitis noninfective	1 (10%)				1 (10.0%)
GI DISORDERS	Dysphagia		1 (10%)			1 (10.0%)
GENERAL/ADM. SITE CONDITIONS	Edema face	1 (10%)				1 (10.0%)
MUSCULOSKELETAL/CONNECTIVE TISSUE	Flank pain	1 (10%)				1 (10.0%)
VASCULAR DISORDERS	Flushing	1 (10%)				1 (10.0%)
GENERAL/ADM. SITE CONDITIONS	General and admin site - Other - Light Headedness	1 (10%)				1 (10.0%)
EAR & LABYRINTH	Hearing impaired	1 (10%)				1 (10.0%)
GI DISORDERS	Hemorrhoids	1 (10%)				1 (10.0%)
VASCULAR DISORDERS	Hot flashes	1 (10%)				1 (10.0%)
SKIN & SUBCUTANEOUS DISORDERS	Hyperhidrosis	1 (10%)				1 (10.0%)
VASCULAR DISORDERS	Hypotension	1 (10%)				1 (10.0%)
RESPIRATORY/THORACIC/MEDIASTINAL	Hypoxia			1 (10%)		1 (10.0%)
INVESTIGATIONS	Investigations - Other, specify - Increase Ldh	1 (10%)				1 (10.0%)
INVESTIGATIONS	Investigations - Other, specify - Methemoglobinemia		1 (10%)			1 (10.0%)
PSYCHIATRIC DISORDERS	Irritability	1 (10%)				1 (10.0%)
MUSCULOSKELETAL/CONNECTIVE TISSUE	Musculoskel/connect tissue -Other - Muscle Cramping	1 (10%)				1 (10.0%)

MUSCULOSKELETAL/CONNECTIVE TISSUE	Musculoskel/connect tissue -Other - Pelvic Muscle Spasm	1 (10%)				1 (10.0%)
MUSCULOSKELETAL/CONNECTIVE TISSUE	Myalgia	1 (10%)				1 (10.0%)
MUSCULOSKELETAL/CONNECTIVE TISSUE	Pain in extremity	1 (10%)				1 (10.0%)
REPRODUCTIVE & BREAST DISORDERS	Pelvic pain	1 (10%)				1 (10.0%)
NERVOUS SYSTEM	Peripheral sensory neuropathy	1 (10%)				1 (10.0%)
RESPIRATORY/THORACIC/MEDIASTINAL	Productive cough	1 (10%)				1 (10.0%)
RENAL & URINARY DISORDERS	Proteinuria	1 (10%)				1 (10.0%)
RENAL & URINARY DISORDERS	Renal & urinary disorders - Other - Bladder Pain	1 (10%)				1 (10.0%)
RENAL & URINARY DISORDERS	Renal & urinary disorders - Other - Pyelonephritis			1 (10%)		1 (10.0%)
RENAL & URINARY DISORDERS	Renal & urinary disorders - Other - Urinary Pressure	1 (10%)				1 (10.0%)
REPRODUCTIVE & BREAST DISORDERS	Reproductive and breast - Other - Dysuria	1 (10%)				1 (10.0%)
REPRODUCTIVE & BREAST DISORDERS	Reproductive and breast - Other - Vaginal Bleeding	1 (10%)				1 (10.0%)
PSYCHIATRIC DISORDERS	Restlessness	1 (10%)				1 (10.0%)
SKIN & SUBCUTANEOUS DISORDERS	Skin & subcutaneous tissue -Other - Dermatitis	1 (10%)				1 (10.0%)
SKIN & SUBCUTANEOUS DISORDERS	Skin & subcutaneous tissue -Other - Parasthesia		1 (10%)			1 (10.0%)
SKIN & SUBCUTANEOUS DISORDERS	Skin & subcutaneous tissue -Other - Skin Patches	1 (10%)				1 (10.0%)
RESPIRATORY/THORACIC/MEDIASTINAL	Sore throat	1 (10%)				1 (10.0%)
GI DISORDERS	Toothache	1 (10%)				1 (10.0%)
RENAL & URINARY DISORDERS	Urinary incontinence	1 (10%)				1 (10.0%)
INJURY, POISONING & PROCEDURAL	Vascular access complication			1 (10%)		1 (10.0%)

Looking only at the highest grade for each Adverse Event experienced by a Patient, this report displays the number of patients that experienced each Adverse Event, by Grade, for each Organ Class and for each Preferred Term within an Organ Class. It also displays the percentage of treated patients in the study that experienced the Adverse Event with that Grade as their highest grade for that event.

### 5.1.3.3 Pharmacokinetics

Summary PK of triapine in the dose escalation is reported below. PK is comparable to earlier reports of triapine for both routes. PO bioavailability observed in this trial was 66%, which is also comparable to previous reports of 67% (Chao 2012). There was no discernable difference between triapine exposure at 100 vs 150 mg PO, and between patient variability at each dose level was substantial.

Pharmacokinetics of triapine at 50 mg IV (left), 100 mg PO (middle) or 150 mg PO (right).

#### Pharmacokinetic parameters of triapine at 50 mg IV.

PT (#)	Cmax (ug/L)	Tmax (h)	HL (h)	AUClast (h*ug/L)	AUCINFobs (h*ug/L)	Extrap (%)	Cl_obs (L/h)	Vss_obs (L)	Vz_obs (L)	Tlast (h)
Geo Mean	294	1.6	1.3	718	734	2.0	68	119	124	10
Geo SD	1.2	1.1	1.3	1.4	1.4	1.7	1.4	1.4	1.3	1.8
N	10	10	10	10	10	10	10	10	10	10

#### Pharmacokinetic parameters of PO triapine.

[figure not shown]
PO_DOSE	PT (#)	Cmax (ug/L)	Tmax (h)	HL (h)	AUClast (h*ug/L)	AUCINFobs (h*ug/L)	%Extrap (%)	Cl_F_obs (L/h)	Vz_F_obs (L)	Tlast (h)
100	GeoMean	520	1.2	1.3	1187	1209	0.8	83	156	14
	GeoSD	2.5	1.6	1.2	2.6	2.5	4.2	2.5	2.6	1.9
	N	6	6	6	6	6	6	6	6	6
150	GeoMean	344	1.5	1.5	990	1034	3.9	145	322	10
	GeoSD	1.9	1.5	1.3	1.4	1.4	1.7	1.4	1.5	1.7
	N	4	4	4	4	4	4	4	4	4

#### Bioavailability of triapine.

[figure not shown]
PO_DOSE		F
100	Geometric Mean	0.75
	Geometric SD	2.2
	N	6
150	Geometric Mean	0.54
	Geometric SD	1.5
	N	4
Overall	Geometric Mean	0.66
	Geometric SD	1.9
	N	10

#### 5.1.3.4 Pharmacodynamics

There was no obvious relationship between occurrence of DLT and triapine AUC. Methemoglobin levels were sampled at approximately 4 h after dosing on PK days, and the observed levels had a clear correlation with triapine exposure both when expressed as AUC and Cmax.

#### 5.1.3.6 Conclusion

Based on the 3+3 design, 100 mg PO daily was determined to be the MTD with 1 out of 6 evaluable patients experiencing a DLT, while 150 mg PO daily resulted in 2 out of 3 evaluable patients with a DLT. The side effect profile at 100 mg PO daily was considered acceptable and consistent with the expected side effect profile of the cisplatin chemoradiation therapy backbone. Exposures were comparable to previous reports (Chao 2012), patients treated at 150 mg did not achieve higher plasma exposures than at 100 mg PO, and patients with DLT did not appear to have markedly different exposures than patients that without DLT.

In summary, 100 mg triapine PO daily in combination with cisplatin based chemoradiation is the appropriate dose to take forward into the expansion phase of this phase 1 trial.

## 5.2 Radiation therapy:

### 5.2.1 Radiation Therapy for Cervical Cancer or Vaginal Cancer

Patients will receive 5 consecutive days of external beam radiation (EBRT) preferably given Monday-Friday, and repeated for 5 consecutive weeks. A three consecutive day parametrial may be given in the sixth week or in the week after completion of chemoradiation if treatment missed in days 1-35 has to be made up. Radiation therapy must be completed within  $56 \pm 3$  days of its initiation (two (2) make-up weeks are permitted).

External beam radiation will be delivered using a linear accelerator with a photon energy of 6 MV or greater. Source-to-axis distance (SAD) of 100 cm is required. Intracavitary therapy could be delivered by low dose-rate (LDR) brachytherapy using  $^{137}\text{cesium}$  or high dose-rate (HDR) brachytherapy using  $^{192}\text{iridium}$ . **Intensity modulated radiation therapy (IMRT) is permitted on this study (see Section 5.2.1.1).**

Localization and Simulation: Patients to be simulated in the supine position with feet tied together for immobilization (may use vacuum-evacuated device if desired). CT simulation is required, if feasible with full and empty bladder (for generation of an internal target volume for the cervical contour when feasible) and an empty rectum. CT scan should extend at least 4 cm above and below the target volumes with inter slice thickness of  $\leq 3\text{mm}$ . Intravenous contrast may be used during simulation to help better define the vessels.

Contouring: The lymph node Clinical target volume (CTV1) includes entire bilateral common iliac, external/internal iliac, upper pre-sacral (from S1-S3) and obturator regions. For patients with pelvic node positive and para-aortic node not surgically staged include the entire para-aortic nodal region up to renal vessels. For patients with para-aortic node positive include the entire para-aortic nodal region up to renal vessels or at least 2 cm above highest para-aortic node. The involved nodes are contoured as GTV and expanded by 5 to 7 mm with editing for the small bowel and duodenal region to create PTV2 for the concomitant boost or sequential boost. Involved nodes are defined as all lymph nodes  $\geq 1\text{cm}$  in the short axis, those with a necrotic center and/or PET avidity

The primary CTV2 included the entire gross tumor plus the entire cervix, uterus, parametria, and proximal  $\frac{1}{2}$  of the vagina (unless vaginal involvement where the entire vagina is included). CTV1 is expanded 5-7 mm to create nodal PTV. CTV2 is expanded by 1.5-2 cm to account for target motion and set up uncertainty to create primary PTV. If ITV created, then 7-10 mm to ITV should be sufficient for primary PTV. Nodal PTV and Primary PTV is combined to create a final PTV1. Involved node with 5 to 7 mm expansion as described would be PTV2. Normal tissue structures will be contoured on the CT scan obtained with a full bladder since treatment will be delivered with a full bladder with the goal of reducing the volume of irradiated bowel. A description for the technique on how to contour these structures can be found at [http://www.rtg.org/CoreLab/ContouringAtlases/FemaleRTOGNormalPelvisAtlas.aspx](http://www.rtog.org/CoreLab/ContouringAtlases/FemaleRTOGNormalPelvisAtlas.aspx).

Bladder will be outlined on every slice, including the portion inferior to the planning target volume. Rectum will be outlined on every slice, including the portion inferior to the planning target volume and superior to the level that it leaves the posterior pelvis around the region of the rectosigmoid. Bowel space will be outlined on every slice which has visible bowel, extending

2 cm above the planning target volume. Bowel space will include the volume surrounding loops of bowel out to the edge of the peritoneum because the bowel may lie within this space at any time throughout the course of treatment. Bowel space will include the ENTIRE bowel, including small bowel, colon and sigmoid, in one bowel bag contour. This contour will be named 'bowel space'. The pelvic bone will be contoured as a surrogate for the bone marrow. The pelvic bone from the superior to the inferior aspect of the PTV can be auto-contoured. This can be accomplished with use of a CT-density-based auto-contouring algorithm. The femoral heads but not femoral necks should be included in the bone marrow contour.

#### 5.2.1.1 Intensity Modulated Radiation Therapy (IMRT) Dose Specifications

*Prescription dose shall be according to the following specifications:*

Planning target volume (PTV1) will receive 45Gy in 25 fractions. Patients will be treated once a day, 5 days a week with a daily fraction size of 1.8Gy. All targets will be treated simultaneously. The dose is prescribed to cover 97% of the PTV1. A volume of at least 0.03 cc within any PTV 1 should not receive > 110% of the maximum prescribed dose. No volume within the PTV that is 0.03 cc or larger can receive a dose that is < 93% of its prescribed dose. Any contiguous volume of 0.03 cc or larger of the tissue outside the PTVs must not receive > 110% of the maximum prescribed dose to the PTV. If PTV2 is created, then it can receive concomitant boost of 55 to 57.5 Gy in 25 fractions or sequential boost to a total dose of 58-60Gy.

IMRT Technical Factors: Megavoltage equipment capable of delivering static intensity modulation with a multileaf collimator or dynamic intensity modulation (using a multileaf collimator or tomotherapy) is required. VMAT is allowed. Six or more fields should be utilized with a minimum source-axis distance of 100 cm. The exception is the use of the tomotherapy unit that uses 80 cm. 6-10 MV energy photon beams should be used.

3D EBRT technique: Four field technique with field borders 7 mm from PTV1 in all directions. Target dose is 45Gy in 25 fractions. The minimum dose to the dose specification point (isocenter or calculation point) is greater than or equal to 43.2Gy Maximum dose to a volume of  $\geq 0.03$  cc of tissue within the convergence of the treatment fields should not exceed 107% of the prescription dose. The PTV2 if created would receive sequential boost to a total dose of 58-60Gy.

Parametrial Boost Fields: The parametrial boost field is an anterior-posterior and posterior-anterior field arrangement. The superior border should be reduced to include only the true pelvis. The upper border of the true pelvis field is defined at the inferior aspect of the sacroiliac joint. The inferior border remains the same as in the pelvis fields or mid obturator foramen. A parametrial central field block is a minimum of 6 cm wide. The dose for parametrial boost is 5.4Gy in 3 fractions.

Dose constraints for IMRT (recommended but not mandated, as below). Priority should be given to PTV1 coverage IMRT arm:

Bowel up to 30-40% receives 40Gy,

Bladder up to 50-60% receives 40Gy

Rectum up to 50-60% receives 40Gy

Bone marrow up to 75-80% receives

NCI Protocol #: 9892

Version Date: January 12, 2023

20Gy

Kidneys for extended field up to < 10% receives 16Gy

In patients with nodal boost V55 Gy for small bowel < 5-15cc and Duodenum V55 < 1cc

**Verification Requirements:** Image should be performed at least weekly for patients treated on the IMRT and standard therapy arms, respectively. For patients treated with IMRT dose delivery, orthogonal films or CBCT to localize the isocenter placement shall be obtained. For patients treated with standard therapy, weekly port films should be obtained. The length of the treatment field shall be indicated on these films. These films will not be collected but should be held by the institution and available for review if requested.

#### 5.2.1.2 Intracavitary Brachytherapy:

At the time of registration, institutions will select the one brachytherapy dose rate to be used for all accrued patients at that institution, either low-dose-rate (LDR) or high-dose-rate (HDR).

**Low Dose Rate (LDR) Brachytherapy:** Following the completion of external beam RT, the patient will receive 4000cGy to Point A or 3D image based brachytherapy following GEC ESTRO guidelines by intracavitary tandem and ovoid implant with cesium. The patient may receive this in one or two applications at the discretion of the radiation oncologist. The first insertion should be performed promptly upon completion of external beam irradiation. If two implants are contemplated, the second implant should be completed within three weeks of the completion of external beam irradiation.

**High Dose Rate (HDR) Brachytherapy:** 3D image based brachytherapy using MRI or CT based planning using GEC ESTRO guidelines. Dose of each brachytherapy fractions is 550- 600cGy for a total 5 or 700 cGy per fraction to total of 4 fractions. HDR brachytherapy should start at week 4 or 5. When HDR brachytherapy begins, at least one insertion will be performed per week with no external beam therapy given on the day of the insertion. If the majority of the external beam radiation has been given, then two or three insertions per week could be done separated by at least 48 to 72 hours in order to complete all treatment within 56 ± 3 days.

**HDR Instruments:** It is recommended that tandem and ovoids or tandem or ring or hybrid applicator be used for HDR brachytherapy for patients with cervical cancer. Interstitial brachytherapy with a Vienna, a Venezia applicator or Syed template should be used for patients with vaginal cancer who are not candidates for intracavitary brachytherapy.

**HDR Dosimetry:** The planned total dose to high risk clinical target volume (HRCTV) after summatting for EBRT and brachytherapy should be EQ2 of 80-90Gy. Similarly total dose to bladder, rectum and sigmoid should be ≤ 80Gy, 65Gy and 70Gy respectively. If intracavitary brachytherapy cannot be performed, then interstitial or hybrid applicator brachytherapy can be performed as per standard institutional guidelines and practice. Reasons for not performing intracavitary brachytherapy should be documented for those patients with cervical cancer.

#### 5.2.1.3 Interstitial Brachytherapy

NCI Protocol #: 9892

Version Date: January 12, 2023

Interstitial brachytherapy such as with a Vienna, Venezia applicator or Syed template is allowed for those patients with vaginal cancer who are not candidates for intracavitary therapy or if it is felt to be clinically imperative to change the plan after treatment start because of poor response of the tumor to external beam therapy.

## 5.3 Chemotherapy

### 5.3.1 Cisplatin

Cisplatin will be given by IV infusion at a dose of  $40 \text{ mg/m}^2$  on days 2, 9, 16, 23, and 30 (Tues) for a total of 5 weekly cycles. It will also be permitted to include a 6th cycle of cisplatin during the parametrial boost or any make-up radiation treatment in a sixth week of external beam radiotherapy. Patients will be strongly encouraged to increase oral hydration 24 hours prior and after chemotherapy administration. Normal saline will be infused IV as pre- and post-hydration to cisplatin infusion as per institutional standard protocol and investigator discretion. Standard premedication with antiemetic, steroid, and H2 blocker will be administered as per institution protocol. Cisplatin  $40 \text{ mg/m}^2$  (maximum dose, 70 mg) may be mixed with mannitol 25 g in 1L normal saline, but sites may also follow institutional practice. It will be infused over 60-120 minutes or per institutional protocol. All patients receive weekly cisplatin on this protocol.

### 5.3.2 Intravenous Triapine

Triapine 50 mg intravenous infusion over 120 +/- 10 minutes is administered once during the study within 90 minutes after pelvic irradiation, on day 1 to obtain PK data. Triapine 50 mg is diluted in 500 mL normal saline or 500 mL 5% dextrose in water and administered using DEHP-free low sorbing infusion set. All patients will receive dexamethasone IV prior to each IV triapine infusion. Premedicate with antiemetic as needed for patients developing nausea or vomiting with a previous dose of triapine.

### 5.3.3 Oral triapine

Oral triapine will be given at the assigned phase I dose level (see 5.1.1 Dose Escalation Schedule). Patients will be asked to fast (except for water) for 2 hours prior to dosing and for 1 hour after ingesting the oral dose (triapine complexes strongly with iron ions). Patients will ingest one dose of triapine in the clinic within 90 minutes after each daily radiation treatment, starting with the first radiation treatment through the last day of radiation treatment (completion of EBRT). Each oral triapine dose will be administered in the clinical area within 90 minutes of each daily RT dose. Triapine will not be administered on days that radiation is not given (Sat- Sun, holidays) or on the days that radiation is missed or held. Study staff will observe and document triapine administration and will document dosing time in the patient's record. The patient will be requested to maintain a medication diary of each dose of medication (see APPENDIX D PATIENT MEDICATION DIARY – TRIAPINE). The medication diary will be reviewed by clinic staff each week.

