## 5.1 Agent Administration

Chemotherapy and Radiation Regimen				
Agent a	Pre-medications; Precautions	Dose	Route	Schedule
Pelvic external beam radiation	Skin, antiemetic, or anti-diarrheal medications may be administered as needed.	1.8 Gy/ day	N/A	Days 1 to 5 (Mon-Fri), Weekly x 5 weeks (25 treatments)
Pelvic brachytherapy (See Section 5.2)	Antiemetic and anti-diarrheal medication may be administered as needed.	30 to 40 Gy in one or multiple fractions using LDR or HDR techniques	N/A	
IV Triapine (See Section 5.3.3 for required clinical monitoring)	All patients will receive dexamethasone IV prior to each IV triapine (3-AP) infusion. Pre-medicate with antiemetic as needed for patients developing nausea or vomiting with a previous dose of triapine.	Fixed dose – 50 mg diluted in 500 ml NS or 500 ml 5% dextrose in water	IV infusion over 120 +/- 10 minutes within 90 minutes after pelvic irradiation using DEHP-free low sorbing infusion set.	Day 1
Oral Triapine (See Section 5.3.3 for required clinical monitoring)	No premedications needed. Antiemetic as needed for nausea or vomiting.	As per assigned Dose Level (see “Dose-Escalation Schedule”, section 5.1.1)	PO taken within 90 minutes of completion of pelvic external beam radiation treatment	Days 2-5, 8-12, 15-19, 22-26, 29-33

Cisplatin	IV hydration before cisplatin and antiemetic and steroid prophylaxis pre-medication as per institution protocol.	40 mg/m  (70 mg maximum), diluted with 25g mannitol in 1L normal saline or per institutional practice.	IV infusion over 60-120 minutes or as per institution protocol using non-aluminum administration sets. Following cisplatin, post-hydration therapy should be administered as per institution protocol.	Once weekly x 5 weeks (Days 2, 9, 16, 23, 30)
-----------	---	--	--	---

aRadiation therapy (RT) and chemotherapy must be administered in the order provided in the above table (Chemotherapy and Radiation Regimen)

Treatment will be administered on an outpatient basis. Appropriate dose modifications are described in Section 6. No investigational or commercial agents or therapies other than those described below may be administered with the intent to treat the patient's malignancy.

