#### Dose Escalation Schedule

Radiation Therapy	Dose Level	IV cisplatin weekly	PO Triapine* Dose / Days / Weekly x5
Pelvic RT + Brachytherapy (+/- Extended Field)	-2	40 mg/m 	50 mg D1,3,5
	-1	40 mg/m 	50 mg QD x5
	1	40 mg/m 	100 mg QD x5
	2	40 mg/m 	150 mg QD x5
	3	40 mg/m 	200 mg QD x5

\*1 of the planned 25 doses of triapine will be delivered IV (day 1) at a fixed dose of 50 mg to allow PK and PD studies (assuming 60% bioavailability and a BSA of 1.73 m^2). If DL-2 needs to be explored, the PK-PD days will be rearranged to the first day of the first 2 weeks of treatment.

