### 5.5 Definition of Dose-Limiting Toxicity

DLTs are defined as the following adverse events if considered at least “possibly related” to a component of the study therapy and which occur from the start of treatment until completion of EBRT, prior to initiation of brachytherapy (i.e. the first 5 weeks if no treatments are missed):

- Any nausea, vomiting, diarrhea and elevation of serum creatinine level Grade 3 toxicity **not resolved with maximal intervention to Grade 0-2 over 7 days (except alopecia and fatigue);**
- Any nausea, vomiting, diarrhea and elevation of serum creatinine level Grade 4 toxicity
- Any other non-hematologic toxicity  $\geq$ Grade 3;
- Any hematologic toxicity of  $\geq$  Grade 4;
- Grade  $\geq$ 3 dyspnea;
- Inability to deliver at least 20 of the scheduled 25 administrations of triapine at the planned dose, **allowing for 2 weeks to make up missed radiation days.**
- Inability to deliver at least 4 of the scheduled 5 administrations of IV cisplatin at the planned dose.

Dose escalation will proceed within each cohort according to the following schema, unless stated otherwise.

Number of Patients with DLT at a Given Dose Level	Escalation Decision Rule
0 out of 3	Enroll 3 patients at the next dose level.
$\geq$ 2	Dose escalation will be stopped. This dose level will be declared the maximally administered dose (highest dose administered). Three additional patients will be enrolled at the next lowest dose level if only 3 patients were treated previously at that dose.
1 out of 3	Enter at least 3 more patients at this dose level. 
 
• If 0 of these 3 patients experience DLT, proceed to the next dose level.
 
• If 1 or more of this group suffer DLT, then dose escalation is stopped, and this dose is declared the maximally administered dose. Three (3) additional patients will be enrolled at the next lowest dose level if only 3 patients were treated previously at that dose.
 

≤1 out of 6 at highest dose level below the maximally administered dose
	
This is generally the Recommended Phase 2 Dose (RP2D). At least 6 patients must be enrolled at the RP2D (section 5.1.2).

--	---

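### Triapine is fixed at 25 administrations in some sections and runs to the end of external beam radiation in others; the two rules, and the DLT window tied to them, diverge when a sequential nodal boost is given

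*Combined protocol and SAP*

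**What the plan says.** **Fixed count.** The Schema and the table in Section 5.1.1 state that "1 of the planned 25 doses of triapine will be delivered IV (day 1) at a fixed dose of 50 mg". Section 5.1 lists the oral days as "Days 2-5, 8-12, 15-19, 22-26, 29-33" and the pelvic course as "Weekly x 5 weeks (25 treatments"). Section 5.5 counts as a DLT the "Inability to deliver at least 20 of the scheduled 25 administrations of triapine at the planned dose". The Section 10 calendar marks triapine in weeks 1 to 5 only, and the Appendix D diary ends at day 35.

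**Event-driven rule.** Sections 5.3.3 and 8.1.2 give one dose after each daily radiation treatment "through the last day of radiation treatment (completion of EBRT"). Neither states a maximum.

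**Radiation beyond 25 fractions.** For involved nodes, Section 5.2.1.1 allows either a concomitant boost within the 25 fractions or a "sequential boost to a total dose of 58-60Gy". It also states: "The dose for parametrial boost is 5.4Gy in 3 fractions". Section 5.3.1 permits a sixth cisplatin cycle during a parametrial boost or make-up radiation, and describes that week as part of external beam radiotherapy. There is no matching sentence for triapine.

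**DLT window.** Section 5.5 runs the window to completion of EBRT, before brachytherapy, and equates this to 5 weeks when nothing is missed. Section 13.2 sets 5 weeks excluding delays. Section 13.3.1 requires a DLT-evaluable patient without a DLT to have received at least 80% of the treatment intended in that window.

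**The concern.** For a patient whose EBRT is extended by a boost, a site following 5.1 stops triapine at 25 administrations. A site following 5.3.3 continues it, and both are following the protocol. The case is foreseeable: stage IIIC is eligible, Section 5.2.1 contours involved nodes for a boost, and for the 3D technique only the sequential boost is named.

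Two things are at stake. The first is investigational-drug exposure that differs between patients for a reason the protocol does not settle. The second is the DLT rate at the RP2D, which 13.3.3 reports with an exact confidence interval and which drives the Bayesian suspension rule in 13.1.1. If the window follows EBRT, some patients are observed for longer, and on more drug, than others. The 5-week statements in 5.5 and 13.2 allow for missed or delayed treatment but not for boosts.

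**Working it through.** **1. The plan's own count.** 45 Gy / 1.8 Gy = 25 fractions. Oral days are 4 + 5 + 5 + 5 + 5 = 24, plus 1 IV = 25. At five fractions a week, fraction *f* falls on day 7 × floor((*f* − 1)/5) + ((*f* − 1) mod 5) + 1, so fraction 25 falls on day 33. The delivery criterion is 20/25 = 80%. The fixed-count sections agree with one another.

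**2. Concomitant boost.** It stays within 25 fractions and adds no administrations.

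**3. Parametrial boost alone.** 5.4 Gy / 3 = 1.8 Gy per fraction. If it is additional, the total is 25 + 3 = 28 (+12%), ending on day 38. If it only replaces missed fractions, as Section 5.2.1 can be read, it need not take the total above 25.

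**4. Sequential nodal boost.** The extra dose is 58 − 45 = 13 Gy to 60 − 45 = 15 Gy. The fraction size *s* is an assumption. Extra fractions are 13/*s* to 15/*s*, rounded to the nearest whole number or up.

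| Assumed *s* (Gy) | 13/*s* | 15/*s* | Extra fractions | Administrations under 5.3.3 | Against 25 | EBRT ends, day |
|---|---|---|---|---|---|---|
| 1.8 | 7.2 | 8.3 | 7–9 | 32–34 | +28% to +36% | 44–46 |
| 2.0 | 6.5 | 7.5 | 7–8 | 32–33 | +28% to +32% | 44–45 |
| 2.2 | 5.9 | 6.8 | 6–7 | 31–32 | +24% to +28% | 43–44 |
| 2.5 | 5.2 | 6.0 | 5–6 | 30–31 | +20% to +24% | 40–43 |

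Over the assumed range this is 30 to 34 administrations, +20% to +36%. Under the fixed count the difference is zero.

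**5. DLT window.** If it follows EBRT, it ends on day 40 to 46 instead of day 33: 40/33 = +21%, 46/33 = +39%. In the other direction, 5.5 places the window before brachytherapy and 5.2.1.2 says HDR should start in week 4 or 5. That could close the window before fraction 25. The documents therefore support a window shorter than, equal to or longer than 5 weeks.

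**6. Delivery against evaluability.** Suppose boost fractions carry triapine, fall inside the window and count as intended treatment.
- 30 due: 80% is 24. A patient with 20 to 23 meets the delivery criterion (20/30 = 67%) but is below 80%.
- 34 due: 80% is 27.2. The same happens with 20 to 27 (20/34 = 59%).

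Such a patient has no DLT on delivery grounds and, without another DLT, is not evaluable under 13.3.1. At 25 due, both thresholds are 20 and no gap exists.

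**The case against.** The strongest reply is that the passages can be read together. Section 5.1 defines the pelvic course as 25 treatments, and 5.3.3 opens by referring to the 5.1.1 table with its 25 planned doses. Completion of EBRT could then simply mean fraction 25. That reading is possible, but the text does not secure it. Section 5.3.1 treats a parametrial-boost or make-up week as a sixth week of EBRT, and no section says that triapine stops before boost fractions.

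Other replies do stand and limit the point:
- The 20-of-25 criterion is an absolute count. It is not wrong in itself; it only parts from the 80% rule when more than 25 are due.
- Staff must observe and document every dose, so doses after day 35 are not lost for want of a diary row.
- Section 5.1.2 already adds 30 days of observation for the six patients at the MTD, and escalation is complete. The open question mainly concerns the expansion cohorts.

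A reader might infer that exposure differs by up to a third across the trial. The documents do not support that: the fraction size is not given, only sequentially boosted patients are affected, and a third is not a ceiling either. At 1.8 to 2.0 Gy, both boosts together would give 35 to 37 administrations (+40% to +48%) if the parametrial boost is additional.

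A reader might also infer a large shift in the DLT rate. With a constant hazard and every patient boosted to 33, a 20% rate becomes 1 − 0.8^(33/25) = 25.5%, and the chance of suspension rises from 0.45 to about 0.68. Neither condition is supported. The boosted share is not given, and Section 2.2.1 reports that 90% of toxicity with the IV regimen occurred in the first 5 weeks.

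**Conclusion.** The inconsistency is real and should be resolved. Two stated rules give different triapine totals whenever EBRT exceeds 25 fractions, and the DLT window and its denominators inherit the conflict. For sequentially boosted patients under the event-driven rule, the difference is about 5 to 9 administrations (+20% to +36%), assuming 1.8 to 2.5 Gy per boost fraction. The parametrial boost adds 3 only if it is additional, and the concomitant boost adds none. The effect on the cohort DLT rate cannot be quantified from the documents. The documents also do not show that any patient received more than 25 administrations. Which dosing rule is right is for the sponsor to decide.

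**What to change.** 1. Reconcile Sections 5.1, 5.3.3, 8.1.2, 10 and Appendix D on the number of triapine administrations, the event that ends dosing, and whether boost and make-up fractions carry triapine. No number or rule is proposed here.
2. Make Sections 5.5, 13.2 and 13.3.1 use one definition of the DLT window. It should say how boosts and an early HDR start are handled. Use one denominator for the delivery criterion and the 80% rule.
3. In 13.3.3, keep the protocol-defined DLT rate. Add, as a supplementary summary, the rate over the common 25-fraction period, with events during boost fractions identified and not dropped. Replacing the main rate with a common-period rate would not be advisable: it could remove late toxicities and would clash with the two make-up weeks in 5.5.

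The cost is wording in eight places, a sentence in 13.3.3 and possibly more diary rows. There are no extra patient procedures; the supplementary rate needs only the dates of fractions and of event onset.
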